**A 20-months surveillance of non-invasive *Streptococcus pneumoniae* infections in Belgium
to evaluate national vaccination strategy**

Protocol Version 1.2

05/12/2019

0 Summary

Population	3,600 Belgian patients with community acquired pneumonia or acute otitis media, leading to positive S. pneumoniae from non-sterile clinical specimens.
Intervention	N/A
Comparison	Serotype distribution according to vaccination programs (campaigns)
Outcome	Primary: to establish insight in serotype dynamics for non-invasive pneumococcal diseases in Belgium (prospectively and retrospectively), in association with changing vaccination programs (campaigns). Secondary: surveillance of emerging serotypes, clones and drug resistances. Study of the genetic divergences between invasive and non-invasive pneumococcal diseases isolates.
Study Type	Observational

Principle Investigator [name]
Coordinating Scientist [name]
Institute Sciensano
Address [name]
Contact [contact] [contact]
[contact] [contact]

1 Study Rationale

1.1 Pneumococcal vaccination programs reduced burden of invasive disease

Streptococcus pneumoniae is a leading cause of morbidity and mortality worldwide among children <2 years of age and in the elderly [1]. The pathogenicity of this bacteria can be divided into 2 forms: invasive (IPD) and non-invasive pneumococcal disease (NIPD). Whereas the dangerous IPD type is responsible for meningitis and bacteraemia (septicaemia), the less severe NIPD can cause upper and lower respiratory tract infections such as community acquired pneumonia (CAP) and otitis media (OM). Of note, this subdivision between IPD and NIPD pneumococcal diseases is somewhat arbitrary since a substantial proportion (10-20%) of CAP pneumonia caused by *S. pneumoniae* is associated with contemporary bacteraemia (especially in elderly and debilitated patients). The distinction between PID and NIPD relates to the laboratory diagnosis and anatomical sites from which pneumococci are isolated. In PID, *S. pneumoniae* is detected from normally sterile body fluids (blood, cerebrospinal fluid (CSF), pleural, peritoneal or articular fluids). In NIPD, pneumococcal isolates are typically isolated from superficial body sites such as ear, nose, sputum or other lower respiratory tract sites (bronchial, endotracheal aspirates, bronchoalveolar lavage,...). There are over 90 pneumococcal serotypes, classified by an immunologically distinct capsule encoded by the capsular polysaccharide (*cps*) biosynthesis locus of the genome. The capsule is a major virulence factor and the basis for the currently licensed vaccines targeted toward the paediatric and elderly communities.

In the course of the decades, various pneumococcal conjugate vaccines were successively introduced, with the 7-valent PCV7 vaccine gradually being replaced by the 10-valent PCV10 and the 13-valent PCV13 [4]. These vaccination programs have led to drastic changes in the global epidemiology of pneumococcal diseases. Spawned surveillance data unequivocally showed strong decreases in IPD rates caused by the PCV serotypes. Simultaneously, serotype replacement by non-vaccine targeted serotypes occupying nasopharyngeal niches vacated after vaccination was observed. A recent example of this is the emergence of multidrug resistant serotype 35B in IPD isolates from USA and France (**Figure 1**) [5-7].

[figure not shown]

Figure 1. Number of serotype 35B invasive isolates by year from 1994 to 2014 in the USA, contrasting declining IPD incidence after vaccination campaigns. Figure from ref. [5].

Further, an important, and as yet underestimated, role is thought to be played by non-encapsulated pneumococcal strains (NeSP), currently not targeted by vaccination. These strains have either deleted or dysfunctional *cps* genes, or have novel genes in place at this locus [8]. NeSP strains have been isolated from patients with invasive and non-invasive pneumococcal disease, but are typically more frequently associated with non-invasive diseases like conjunctivitis (85%) and OM (8%) [9].

1.2 Changing vaccination recommendations in Belgium

In Belgium, the 23-valent polysaccharide vaccine or PPV23 (currently Pneumovax 23®, MSD) is licensed since 1995. It is currently recommended by the Superior Health Council (CSS/HGR) for the prevention of pneumococcal infections in persons ≥ 2 years of age, presenting with an increased risk of mortality and severe morbidity due to pneumococcal infections, and often sequentially combined with PCV13 (Prevenar®, Pfizer) [4]. The national infant vaccination program was initiated in 2007 with PCV7 (Prevenar®, Pfizer), and was updated to PCV13 in 2011. In 2015-2016, the program changed from PCV13 to PCV10 (Synflorix®, GSK). Very recently (HGR 9519, December 2018), a new advice was published by the Superior Health Council which recommended again the use of the 13-valent vaccine in children ≤ 2 years of age, alongside an explicit statement stating that this advice could be reconsidered upon the release of new data.

1.3 The underdiagnosed and non-surveilled non-invasive population

Current national and international pneumococcal surveillance is strongly focused on IPD. However, it is now commonly accepted that NIPDs by far account as the major part of all pneumococcal infections worldwide. O'Brien and colleagues reported in 2009 that out of 14.5 million pneumococcal cases, 95.6% were cases of NIPD [1]. In a more recent meta-study by the Johns Hopkins School of Medicine, it was estimated that for every adult bacteraemia case there are at least three non-invasive pneumococcal infections [10], resulting in huge societal and economic costs [11].

Impelled by the lack of surveillance on NIPD, the majority of studies on pneumococcal vaccine effectiveness and serotype replacement are based on IPD data. However, **sheer extrapolation of IPD dynamics to NIPD has been called into question by recent studies**, using serotype-specific urinary antigen technology, which indicated discrepancy between persistent pneumococcal serotypes and the decline of the same serotypes causing IPD [12-14]. To get more insights in this matter, the Belgian Health Care Knowledge Centre (KCE) recently reviewed four observational studies from Denmark, Spain and Portugal (2), and the placebo arm of the CAPITA randomized controlled trial in the Netherlands [15-20]. In the infant populations of the study sites, PCV vaccine choice over time (PCV7, PCV10 and PCV13) and uptake differed. Three studies limited the detection of non-bacteraemic pneumonia to pneumonia with a positive culture of airway respiratory samples such as sputum or broncho-alveolar fluid, while the remaining study used both respiratory and urinary samples. Despite these differences, all studies concluded that the serotype distribution of bacteraemic and non-bacteraemic pneumococcal disease differed substantially in terms of vaccine serotype coverage (**Figure 2**) [15].

[figure not shown]

Figure 2. Proportion of serotype categories in bacteraemic/invasive pneumonia (BP) and non-bacteraemic/non-invasive pneumonia (NBP) in the Netherlands [16], Denmark [17], Spain [18] and Portugal [19,20]. Figure from the Belgian CSS/HGR rapport [15].

These results concurred with the few non-EU studies conducted in USA, Britain and Korea, showing that frequencies of vaccine serotypes among NIPD vary between 28.2 and 57.4%, depending on the specimen type and patient age [21-23].

[figure not shown]

Figure 3. Situation in Belgian infants (<2y). ***serotypes present PCV13 which are absent in PCV10. Data from the Belgian NRC for pneumococcal diseases.

In Belgium, 78.4% of all IPD infections in 2017 were caused by non-vaccine targeted serotypes, which is more than what is found in our neighbouring countries. In infants below 2y, this figure drops to 64.2% in 2018 (**Figure 3**). No information on serotype distributions for NIPD are available.

1.4 Sciensano holds historical collection of non-invasive pneumococcal isolates

Between 1995 and 2015, [name] (MD, PhD) led a team at Sciensano investigating the evolution of antibiotic resistance in NIPD isolates from CAP patients (as well as from children with acute otitis media). For 12 consecutive winter periods, his team collected between 300 and 500 clinical isolates using a network of 15 peripheral hospital-based laboratories distributed across the country. Consequently, we hold a collection of >5,000 strains for which extracted gDNA, complete phenotypic MIC profiles and associated metadata are already available (**Figure 4** for age distribution). This study, funded by Bayer, focused on antimicrobial resistance and did not routinely include serotyping.

This constitutes an extremely valuable collection that dates from before the introduction of pneumococcal vaccination programs. In the context of the proposed study, this collection would serve to retrospectively assess the impact of successive vaccination campaigns on serotype distribution among NIPD isolates in Belgium.

[figure not shown]

Figure 4. Age distribution of the patients for which cultures were included during the NIPD surveillance study in 2012-2013 using the same network of laboratories [24].

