4.1 Prospective track

Regarding the prospective track (**Figure 6**), each month from September 2020 to May 2022 (20 months), twelve laboratories listed in **Table 1** committed to send the first 15 unduplicated isolates of *S. pneumoniae* collected from patients meeting the following criteria:

Inclusion criteria:

- Patients living in Belgium at the time of the study,
- from whom unduplicated *S. pneumoniae* isolates were collected in routine practices,
- from non-invasive upper (e.g.: pus/fluid from nasal sinus or from otitis media fluid) or lower respiratory tract (e.g. sputum bronchial or endotracheal aspirate, bronchoalveolar fluid (BAL),...) clinical samples.
- from patients diagnosed with pneumonia, sinusitis and otitis.

Exclusion criteria:

- Patients for whom *S. pneumoniae* was simultaneously isolated from blood or another usually sterile specimen.

Consequently, a theoretical maximal amount of 3,600 non-invasive *S. pneumoniae* isolates will be prospectively collected, although the actual number will probably be lower given the lower prevalence of NIPD during the summer period. For every shipped strain (with associated metadata) during the study period, the laboratory will be compensated by payment of €20.

The transfer of the isolates (under dry ice) from hospital laboratories to the “Sciensano Unit ‘Antibiotics & Resistance’ (Site Engeland - [name])” will be organised in the last week of every month, using the Sciensano internal sample transport service. Isolates will be accompanied by an electronic record sheet, listing the following metadata **upon availability** :

- isolate number
- Hospitalised (HOS), residing in a long-term care facility (LCF), ambulatory (AMB), or other (to be specified).
- admission date (hospitalised patients only)
- date of specimen collection
- patient age
- patient sex
- sample source including collection method
- clinical diagnosis
- vaccination status of the patient for *Streptococcus pneumoniae*
- For bacterial cultures from sputum, the amount of epithelial cells and white blood samples
- Other potential respiratory pathogens isolated (e.g. *H. influenzae*, *M. pneumoniae*, ...)

For all isolates sent, following analyses will be performed at Sciensano:

- Identification and confirmation of isolates by reference methods prior to use.
- Capsular typing using an FT-IR based method that will be developed in the scope of the project (section 5.4).

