4.2 Retrospective track

As described in Section 1.4, Sciensano holds a collection of >5,000 NIPD strains (1995-2015) for which extracted gDNA, complete MIC profile and associated metadata are already available. From every uneven year, we will randomly select 150 isolates, without bias towards age and gender. On these strains, we will perform FT-IR capsular typing, which will have been developed during the first months of this project (section 5.4). Typing of the isolates of the retrospective study will be performed in the summer period of 2021, when few isolates of the ongoing prospective study (2020-2022) are expected.

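### Section 6.2 pools winter-only historical isolates with year-round 2020-22 isolates in one trend test, so sampling season changes exactly at the step to 2020-22; a contrast matched on calendar months should be added.

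*Protocol*

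**What the plan says.** **Historical track.** Section 1.4 says: "For 12 consecutive winter periods, his team collected between 300 and 500 clinical isolates using a network of 15 peripheral hospital-based laboratories". The isolates are described as "NIPD isolates from CAP patients (as well as from children with acute otitis media", with sinusitis not named. Section 4.2 draws the study sample from this collection: "From every uneven year, we will randomly select 150 isolates, without bias towards age and gender". Month and diagnosis are not part of that rule.

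**Prospective track.** Section 4.1 has "each month from September 2020 to May 2022 (20 months), twelve laboratories listed in" Table 1 send their first 15 isolates per month, "from patients diagnosed with pneumonia, sinusitis and otitis". The summary (section 0) still gives the population as community-acquired pneumonia or acute otitis media.

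**Season.** It is mentioned only for isolate numbers. Section 4.1 expects that "the actual number will probably be lower given the lower prevalence of NIPD during the summer period". Section 4.2 places the retrospective typing in summer 2021, "when few isolates of the ongoing prospective study (2020-2022) are expected".

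**Analysis.** The first bullet of section 6.2 is a chi-square trend analysis that combines the 1995-2014 and 2020-2022 data. The second bullet gives prevalence ratios with Fisher tests within strata of age, gender and infection type. Both stand under a heading that covers the prospective and retrospective tracks. Season appears in neither, and the second bullet does not say that its strata apply to the comparison of periods.

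**The concern.** The main objective (section 2) is serotype dynamics in association with changing vaccination programmes. Section 6.1 sizes a significant shift between the retrospective and prospective samples. All historical isolates are winter isolates, while the 2020-22 isolates come from every month. Season of sampling is thus tied to the last step of the trend. If the serotype mix outside winter differs from the mix in winter, the difference enters that step in full and nothing in the named test separates it from a vaccination effect.

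Only the step to 2020-22 is exposed. Comparisons within the historical series, which spans the programme changes of 2007 and 2011 in section 1.2, stay winter against winter.

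**Working it through.** **Inputs from the protocol**
- PCV13 share (6.1): 7.5 + 7.5 + 5 + 30 = 50%.
- Isolates per period (6.1): 1,500. For the historical track this equals 10 uneven years (1995-2013) x 150, and the budget also lists 1,500. As a sample size for 50% vs 40%, 1,500 is not reproduced (388 per period suffice at 80% power, 641 at 95%, two-sided 5%). That is a separate matter, and 1,500 is taken as given here.
- September 2020 to May 2022 names 21 calendar months (the text says 20). Twelve of them fall in October-March and 6 in December-February. The protocol does not define winter.

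**Assumed, because the documents give no figure**
- The non-winter share of prospective isolates and the winter/non-winter difference in PCV13 share.
- Two-sided 5% level, calendar-year scores, all prospective isolates scored 2021.

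**Step 1: bias.** Bias = non-winter share x seasonal difference.
- Any share x 0 points = 0.
- 10% x 5 points = 0.5 points.
- 10% x 10 points = 1.0 point.
- 20% x 10 points = 2.0 points.

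**Step 2: effect on the trend test.** The Cochran-Armitage statistic is z = Σ nᵢ(tᵢ − t̄)pᵢ / √[p̄(1 − p̄) Σ nᵢ(tᵢ − t̄)²].
- The historical mean year is 2004 and the prospective score is 2021, so t̄ = 2012.5.
- Σ nᵢ(tᵢ − t̄)² = 150 x 330 + 3,000 x 8.5² = 49,500 + 216,750 = 266,250.
- For a bias d at the last step the numerator is 1,500 x 8.5 x d = 12,750d. The denominator is √(0.25 x 266,250) = 258.
- Rejection with no true change ≈ Φ(z − 1.96) + Φ(−z − 1.96).

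| Bias (points) | z | Trend test rejects | Two-sample test rejects |
|---|---|---|---|
| 0 | 0 | 5% | 5% |
| 0.5 | 0.25 | 6% | 6% |
| 1.0 | 0.49 | 8% | 8.5% |
| 2.0 | 0.99 | 17% | 19.5% |

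Simulation of the trend test (200,000 runs) gives 5.0, 5.6, 7.9 and 16.9%, in agreement.

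**Step 3: what a month-matched contrast leaves.** Ceiling = months x 12 laboratories x 15 isolates.
- October-March: 12 x 12 x 15 = 2,160.
- December-February: 6 x 12 x 15 = 1,080.

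Power of the two-sample test = Φ[(d − 1.96·SE₀)/SE₁], with SE₀ pooled and SE₁ unpooled, against 1,500 historical isolates:

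| Prospective isolates | 50% vs 40% | 50% vs 45% |
|---|---|---|
| 1,500 | >99.9% | 78% |
| 1,080 | 99.9% | 71% |
| 540 | 98% | 51% |
| 300 | 89% | 35% |

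For 50% vs 45% as a pure step at 2020-22, the trend test has less power: 69.7, 60.5, 38.6 and 23.0% in the same order.

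**The case against.** **No seasonal serotype difference is documented.** This stands. Sections 4.1 and 4.2 speak of counts only. A reader might infer that the trend is biased by season; the documents support only that it could be, by an unknown amount that includes zero.

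**A large effect needs equal yield in all months.** With 9 of 21 months outside October-March the non-winter share would be 43%. With an assumed 10-point difference the bias would then be 4.3 points and rejection 56%. The protocol expects few summer isolates, which argues against that share. It is silent on the spring and early-autumn months, so the share stays open.

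**Case mix is already handled.** This largely stands. A reader might infer that sinusitis in 4.1 against pneumonia and otitis media in 1.4 is an uncontrolled imbalance. But age and infection-type strata are listed under the heading that covers both tracks, and the historical mix is known from one background sentence, not from eligibility criteria. What remains is that the text does not tie the strata to the period contrast. Nor can a diagnosis effect be sized from section 1.3, where "frequencies of vaccine serotypes among NIPD vary between 28.2 and 57.4%, depending on the specimen type and patient age". That range is attributed to specimen type and age, not diagnosis, and comes from a few non-EU studies.

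**This is detail for the analysis plan.** Partly right: a stratified trend test exists and may be specified elsewhere. But the protocol itself fixes the two unlike collection calendars and their joining, and its own list of strata omits season.

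**Conclusion.** The point holds as a design weakness at one step. The historical isolates are from winter, the prospective ones from all months, and section 6.2 joins them without restricting or stratifying on season. A shift at 2020-22 therefore cannot be cleanly separated from the change in sampling calendar.

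The size cannot be derived from the documents. A bias of 0.5-2 points would move the false-positive rate of the trend test from 5% to about 6-17%. This assumes a 50% PCV13 share, 1,500 isolates per period and the non-winter shares and differences stated above. With no seasonal difference there is no bias.

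It should be fixed because the remedy is cheap, not because harm is shown. Confidence is medium.

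**What to change.** In section 6.2:

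1. Add a retrospective-prospective contrast restricted to prospective isolates from the same calendar months as the historical surveys. Take those months from the historical metadata and state them.
2. State that the age and infection-type strata of the second bullet apply to this contrast. Show diagnoses without a historical counterpart (possibly sinusitis) separately.
3. Report the all-isolate trend beside it, and keep the full year-round set for the 2020-22 proportions.
4. Reconcile the population in the summary with the criteria in section 4.1.

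Restriction is the only route for season. Standardising is not possible, because the historical track has no non-winter isolates.

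**Cost.** No new data items: specimen date, diagnosis and age are already on the record sheet in 4.1, and section 4.2 says historical metadata are available. It does not list the fields, so month and diagnosis must be confirmed there. Prospective metadata come only as available, so some dates or diagnoses will be missing. The contrast uses at most 2,160 or 1,080 prospective isolates, depending on how winter is defined. Two-sample power for 50% vs 40% stays at 89% or more down to 300 isolates. For 50% vs 45% the loss is real, so a null result in the restricted contrast should not be read as no change.

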1.5 Implications for empiric treatment guidelines?

Penicillin and macrolides have been the mainstay in the treatment of respiratory diseases for decades [25], but the worldwide spread of drug-resistant clones translated into increased usage of fluoroquinolones [26,27]. Recently, the World Health Organisation (WHO) included penicillin-resistant *S. pneumoniae* in the list of 12 critical drug-resistant pathogens [28]. Nevertheless, current empiric treatment guidelines support the continued use of penicillin and amoxicillin for drug-susceptible isolates. For risk patients, Belgian Antibiotic Policy Coordination Committee (BAPCOC) recommends use of either a respiratory fluoroquinolone, or combination therapy with beta-lactam antibiotic (high-dose amoxicillin, amoxicillin-clavulanate, or, alternatively, a second- or third-generation cephalosporin) plus a macrolide [29].

Reminiscent of the studies on serotype replacement and global surveillance, studies on pneumococcal drug-resistance are strongly biased towards IPD isolates. However, it is conceivable that the non-invasive population functions as a ‘laboratory’ for the development of drug resistance. During a nation-wide multicentre survey spanning nearly two decades (1995-2014), researchers from Sciensano unequivocally reported higher rates of antibiotic resistance in the non-invasive population, as compared to the invasive strains (**Figure 5**) [30]. Therefore, including antimicrobial resistance screening for non-invasive strains would improve pneumococcal surveillance, improve empiric treatment guidelines and add the possibility to detect circulating drug-resistant clones.

[figure not shown]

Figure 5. Drug non-susceptibility in invasive versus non-invasive *S. pneumoniae* isolates in Belgium (2004-2013). Data from IPD is annually reported by the National Reference Centre for pneumococcal disease. Data for NIPD was collected in the framework of the multicentre study (1995-2014) on drug susceptibility of non-invasive *S. pneumoniae*.

1.6 Key points

From the information above, it is clear that:

- Current recommendations for vaccination and empiric treatment are strongly influenced by the current surveillance focus on IPD. Information on serotype distribution and drug resistance dynamics in NIPD is scarce. However, a discrepancy in serotype distribution between IPD and NIPD isolates is present in neighbouring countries.
- In Belgium, there was a recent (2015-2016) switch in the infant vaccination program to PCV10 and a recommended reversal to PCV13 in December 2018. The influence on serotype distributions in NIPD is unclear, although this information is essential in vaccine cost-effectiveness analyses [31].

2 Study aims

The main objective of this study is to generate insight in the serotype dynamics for NIPD in Belgium, in association with changing vaccination programs. We aim to serotype non-invasive *S. pneumoniae* isolates prospectively collected in Belgian routine laboratories, during a period of 20 months. Simultaneously, a similar characterisation study will be performed retrospectively on a selection of more than 5,000 NIPD strains collected between 1995 and 2014 in Belgium.

Additionally, this projects aims to do the surveillance of emerging serotypes, clones and drug resistances. Using Whole Genome Sequencing (WGS), the genetic divergences between IPD and NIPD isolates will also be studied, in collaboration with the National Reference Centre (NRC) for pneumococcal diseases (UZ Leuven, Belgium).

3 Type of study

This will be an observational study collecting data on *S. pneumoniae* serotypes causing NIPD in Belgium, in relation with changing vaccination programs.

4 Conducting the study

The study will be conducted by Sciensano in collaboration with the NRC for pneumococcal diseases and 12 peripheral clinical laboratories, which all agreed in writing to prospectively collect non-invasive *S. pneumoniae* samples in the framework of this study. These labs are geographically spread over Belgium to avoid clonal bias in sampling (**Table 1**).

Table 1. Peripheral network of participating clinical laboratories.

Hospital	Contact	City	
CHR Citadelle	Dr. [name]	Liège	
CHU Mont-Godinne	Dr. [name]	Yvoir	
ZNA	Dr. [name]	Antwerpen	
Virga-Jessaziekenhuis	Dr. [name]	Hasselt	
Hôpital de Jolimont	Dr. [name]	Haine-St.-Paul	
AZ Delta	Dr. [name]	Roeselare	
AZ St. Jan	Dr. [name]	Brugge	
AZ. Jan Palfijn	Dr. [name]	Gent	
Imeldaziekenhuis	Dr. [name]	Bonheiden	
Hôpital Princesse Paola	[name]. [name]	Marche-en-Famenne	
Clinique St. Joseph	Dr. [name]	Arlon	
CHU de Charleroi	Dr. [name]	Charleroi	

The proposed project workflow is schematically depicted in **Figure 6**. All stages in this work will be performed according to ISO15189 standards.

[figure not shown]

Figure 6. Study design.

